6.1.2 DOSE ADJUSTMENTS FOR TOXICITY

Patients should be assessed clinically for toxicity at each visit using the NCI CTCAE v5.0 (<http://evs.nci.nih.gov/ftp1/CTCAE>) grading scale. Dosing should occur only if a patient's clinical assessment and laboratory test values are acceptable.

Dose Delay/Modifications: Ublituximab

- No reduction in the dose of ublituximab is permitted.
- Supportive care should be considered for any patient who experiences Grade ≥ 2 cytopenias, or Grade ≥ 1 non-hematologic toxicities.
- Ublituximab should be discontinued if treatment is delayed for greater than 56 days due to toxicity.
- If the patient withdraws consent or has documented progression, an end of study visit should be completed.
- If Grade 4 anaphylaxis is observed at any point during ublituximab treatment, permanently discontinue ublituximab treatment and intervene as per investigator discretion.
- For patients with a prior history of hepatitis B and for those with a positive anti-HBc with negative HBsAg at screening who experience an increase in liver enzymes while on study, hold ublituximab immediately and assess for active hepatitis B infection.
 - If negative for hepatitis B, ublituximab may be resumed.
 - If reactivation of hepatitis B is confirmed, institute hepatitis B antiviral treatment. Ublituximab may be resumed at investigator discretion once hepatitis B infection has resolved, with continued monitoring as described above.

Table 2: Ublituximab Dose Delay and/or Modifications Guidance

NCI-CTCAE Grade	Dose Delay and/or Modification
Hematologic Adverse Event	
Neutropenia	
Grade ≤ 3 neutropenia	Maintain current dose. Consider supportive care as warranted.
Grade 4 neutropenia or occurrence of neutropenic fever or infection	Delay ublituximab until Grade ≤ 3 and/or neutropenic fever or infection is resolved; consider growth-factor support as warranted; thereafter, resume at full dose. If delay is > 56 days, discontinue ublituximab.
Thrombocytopenia	
Grade ≤ 3 thrombocytopenia	Maintain current dose and provide supportive care as clinically warranted.

Grade 4 thrombocytopenia	Delay ublituximab until Grade \leq 3; consider intervention with supportive care as warranted; thereafter resume at full dose. If delay is $>$ 56 days, discontinue ublituximab.
Non-Hematological Adverse Events*	
Grade \leq 2	Maintain current dose.
Grade \geq 3	Withhold ublituximab until Grade \leq 2 at the discretion of the investigator; consider supportive care intervention as warranted. Resume at full dose or if delay $>$ 56 days, discontinue ublituximab.

*See guidance above under **Dose Delay/Modifications: Ublituximab** for patients with a prior history of hepatitis B and for those with a positive anti-HBc with negative HBsAg at screening who experience an increase in liver enzymes while on study

Dose Delay/Modifications: Umbralisib

- Supportive care should be considered for any patient who experiences Grade \geq 2 cytopenias, or Grade \geq 1 non-hematologic toxicities.
- Umbralisib should be discontinued if treatment is delayed for greater than 56 days due to toxicity.
- If the patient withdraws consent or has documented progression, an end of study visit should be completed.

Table 3: Umbralisib Dose Delay and/or Modifications Guidance

NCI-CTCAE Grade	Dose Delay and/or Modification
Neutropenia	
Grade \leq 2 neutropenia	Maintain current dose. Consider supportive care as warranted.
Grade 3 neutropenia	Maintain current dose, consider supportive care. If recurrence or persistent Grade 3, resume at next lower dose level at discretion of the investigator.
Grade 4 neutropenia or occurrence of neutropenic fever or infection	Delay umbralisib until Grade \leq 3 and/or neutropenic fever or infection is resolved; thereafter, resume at current dose. Consider supportive care. If recurrence after re-challenge, delay umbralisib until Grade \leq 3 and/or neutropenic fever or infection is resolved; thereafter, resume umbralisib at current dose or at next lower dose level at discretion of the investigator.
Thrombocytopenia	
Grade \leq 3 thrombocytopenia	Maintain current dose level and provide supportive care as clinically warranted.

NCI-CTCAE Grade	Dose Delay and/or Modification
Grade 4 thrombocytopenia	
Delay umbralisib until Grade ≤ 3; thereafter, resume at current dose. Consider supportive care intervention as warranted. If delay is > 56 days, discontinue umbralisib.
 
If recurrence after re-challenge, delay umbralisib until Grade ≤ 3; thereafter, resume umbralisib at current dose or at next lower dose level at discretion of the investigator.

Pulmonary & Related Infections*	
Grade 1 or 2	
Provide supportive care as warranted.
 
Stop all therapy and hold until complete resolution. Restart umbralisib at one lower dose level. Restart ublituximab at full dose.
 
If recurrence after re-challenge, discontinue umbralisib.
 
If applicable, hold ublituximab. Upon resolution, resume ublituximab at full dose and schedule.

Grade ≥ 3	
Provide supportive care as warranted.
 
Discontinue umbralisib and ublituximab.

*For sinopulmonary infections clearly not related to immune-mediated pneumonitis, umbralisib may be continued at investigator's discretion. While pneumonitis has been minimal with umbralisib, it is a reported adverse event associated with other PI3K delta inhibitors. Use of anti-pneumocystis and anti-herpetic viral prophylaxis is required prior to the start of therapy.
	
Liver Injury (ALT/SGPT, AST/SGOT, Bilirubin, Alkaline Phosphatase)	
Grade 1	
Maintain current umbralisib dose.
 
Assess concomitant medications and risk factors*.
 
Monitor labs every 1-2 weeks.
 
Maintain full dose and schedule of ublituximab, if applicable.***

NCI-CTCAE Grade	Dose Delay and/or Modification
Grade 2	
Maintain current umbralisib dose level. Assess concomitant medications and risk factors*. Begin supportive care (prednisone 0.5-1.0 mg/kg/day or equivalent per investigator discretion) **. Monitor labs at least weekly until Grade 1. Once resolved to Grade ≤ 1, taper prednisone by 10 mg per week until off.
 
Maintain full dose and schedule of ublituximab, if applicable.***
 
If liver toxicity recurs to Grade 2:
 
 ○ Re-initiate steroids. ○ Monitor labs at least weekly until Grade 1. ○ Consider delaying umbralisib. ○ If applicable, consider delaying ublituximab.*** ○ Once resolved to Grade ≤ 1 
 ○ If umbralisib was delayed, restart umbralisib at current dose. ○ If applicable: if ublituximab was delayed, restart ublituximab at full dose and schedule.*** ○ Taper prednisone by 10 mg per week until off.
Grade ≥ 3	
Delay umbralisib. Assess concomitant medications and risk factors*. Begin/continue supportive care (prednisone 0.5-1.0 mg/kg/day or equivalent per investigator discretion) **. Monitor labs at least weekly until Grade 1.
 
Once resolved to Grade ≤ 1:
 
 ○ Restart umbralisib at one lower dose level. ○ Taper prednisone by 10 mg per week until off. 
If applicable, delay ublituximab until \leq grade 1; thereafter, resume ublituximab at full dose and schedule.***

* Assess for disorders of lipids and glucose, thyroid disorders, alcohol use, viral infections, etc.
 
**Supportive Care – Aggressive management of lipid, glucose, other metabolic disorders, viral infections, etc.
 
Important: Before initiating steroids, check for viral hepatitis or CMV infection.
 
***See guidance above under Dose Delay/Modifications: Ublituximab for patients with a prior history of hepatitis B and for those with a positive anti-HBc with negative HBsAg at screening who experience an increase in liver enzymes while on study.
	

Diarrhea and/or Colitis
	

NCI-CTCAE Grade	Dose Delay and/or Modification
Diarrhea Grade \leq 2	
Provide supportive care as warranted.
 
If tolerable, maintain current dose of umbralisib. Otherwise, delay umbralisib until \leq grade 1. Resume umbralisib at current dose level.
 
If recurrence after rechallenge, delay umbralisib until \leq grade 1; thereafter, resume umbralisib at current dose or at next lower dose level at discretion of the investigator.
 
NOTE: If persistent grade 2 diarrhea despite supportive care, delay umbralisib until \leq grade 1; thereafter, resume umbralisib at current dose or at next lower dose level at discretion of the investigator.
 
If umbralisib is delayed for $>$ 2 cycles at any time, discontinue umbralisib.
 
If applicable, maintain full dose and schedule of ublituximab. If intolerable or persistent grade 2 diarrhea despite supportive care, delay ublituximab until \leq grade 1; thereafter, resume ublituximab at full dose and schedule. If ublituximab is delayed for $>$ 2 cycles at any time, discontinue ublituximab.

Diarrhea Grade \geq 3	
Provide supportive care as warranted.
 
Delay umbralisib until Grade \leq 2; thereafter, resume umbralisib at current dose or at next lower dose level at discretion of investigator
 
If recurrence after rechallenge, delay umbralisib until Grade \leq 1; thereafter, resume umbralisib at current dose or at next lower dose level at discretion of the investigator.
 
If umbralisib is delayed for $>$ 2 cycles at any time, discontinue umbralisib.
 
If applicable, delay ublituximab until \leq grade 2 (or until \leq grade 1 for recurrence after rechallenge); thereafter, resume ublituximab at full dose and schedule. If ublituximab is delayed for $>$ 2 cycles at any time, discontinue ublituximab.

NCI-CTCAE Grade	Dose Delay and/or Modification		
	Provide supportive care as warranted.		
Colitis (all Grades)	
Delay umbralisib. Treat with supportive care and after resolution of colitis, resume umbralisib at next lower dose level.
 
If umbralisib is delayed for > 2 cycles at any time, discontinue umbralisib.
 
If applicable, delay ublituximab until resolution; thereafter, resume ublituximab at full dose and schedule. If ublituximab is delayed for > 2 cycles at any time, discontinue ublituximab.
		
All Other Non-Hematological Adverse Events			
Grade \leq 2	
Maintain current dose level.
 
Provide supportive care as warranted.
		
Grade \geq 3	
Provide supportive care as warranted.
 
Delay umbralisib until Grade \leq 2; thereafter, resume umbralisib at current dose.
 
If recurrence after re-challenge, delay umbralisib until Grade \leq 2; thereafter, resume umbralisib at current dose or next lower dose level at discretion of the investigator.
 
If umbralisib is delayed for > 2 cycles at any time, discontinue umbralisib.
		
Umbralisib Dose Reduction Recommendations			
Study Drug	Starting Dose	1 st Dose Reduction	2 nd Dose Reduction
Umbralisib	800 mg	600 mg	400 mg

A maximum of two dose level reductions are allowed for umbralisib.
 
If a patient requires a dose reduction of umbralisib due to study drug related toxicity, the dose may not be re-escalated. If further evaluation of the toxicity reveals the event was not related to umbralisib, this must be recorded in the medical record and dose re-escalation to the next higher dose level may be considered at the discretion of the investigator.
 
On the combination treatment, if ublituximab is discontinued due to toxicity, umbralisib should be continued through 12 cycles as planned. If umbralisib is discontinued due to toxicity, ublituximab may be continued at investigator discretion. Any questions related to discontinuation of treatment should be directed to the Principal Investigator, and
			

NCI-CTCAE Grade	Dose Delay and/or Modification
patients should not be discontinued from both ublituximab and umbralisib due to toxicity without discussion with the Principal Investigator.	

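### During combination therapy, Tables 2 and 3 give conflicting ublituximab instructions for pulmonary events, low-grade colitis and some Grade 2 diarrhoea, and no rule says which table governs

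*Combined protocol and SAP*

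**What the plan says.** Section 6.1.2 sets out toxicity rules in two tables. The first is headed "Table 2: Ublituximab Dose Delay and/or Modifications Guidance". Neither its title nor its text limits it to single-agent induction. Apart from cytopenias it has one general rule. At Grade 2 or lower the instruction is "Maintain current dose". At Grade 3 or higher ublituximab is withheld until Grade 2 or lower "at the discretion of the investigator; consider supportive care intervention as warranted. Resume at full dose", with discontinuation if the delay exceeds 56 days.

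Table 3 is titled for umbralisib, but its organ-specific rows also instruct on ublituximab. For pulmonary events of Grade 1 or 2 it says "Stop all therapy and hold until complete resolution"; for Grade 3 or higher, "Discontinue umbralisib and ublituximab". For colitis of any grade it says "If applicable, delay ublituximab until resolution; thereafter, resume ublituximab at full dose and schedule". The liver and diarrhoea rows carry their own ublituximab instructions.

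The notes closing Table 3 add that, on combination treatment, "if ublituximab is discontinued due to toxicity, umbralisib should be continued through 12 cycles as planned". The same paragraph requires discussion with the Principal Investigator before both drugs are stopped for toxicity. A footnote to the pulmonary row lets umbralisib continue, at the investigator's discretion, for sinopulmonary infection clearly unrelated to immune-mediated pneumonitis. It does not mention ublituximab.

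**The concern.** A patient on the combination falls under both tables. Where they disagree, staff following one will breach the other, and the protocol gives no order of precedence. In the sharpest case one table permanently stops a drug that the other resumes at full dose, for the same serious event.

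The events are not marginal. Pneumonitis and colitis of Grade 3 or higher are among the combination toxicities that can halt the study (sections 4.1 and 8.5). At stake are patient safety, consistent ublituximab exposure, and a clear standard for what counts as a protocol-directed delay or discontinuation and what counts as a deviation.

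**Working it through.** The plan states no figure to reproduce. The check sets the ublituximab instruction in Table 2 beside that in Table 3, row by row.

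| Situation | Table 2 | Table 3 | Result |
|---|---|---|---|
| Pulmonary, Grade 1-2 | maintain | stop until fully resolved, then full dose | opposed |
| Pulmonary, Grade ≥3 | withhold to Grade ≤2, resume | discontinue | opposed |
| Colitis, Grade 1-2 | maintain | delay until resolved | opposed |
| Diarrhoea, intolerable or persistent Grade 2 | maintain | delay to Grade ≤1 | opposed |
| Liver, recurrent Grade 2 | maintain | delay is optional | differs |
| Liver, Grade ≥3 | resume at Grade ≤2 | resume at Grade ≤1 | differs |
| Diarrhoea, recurrent Grade ≥3 | resume at Grade ≤2 | resume at Grade ≤1 | differs |
| Colitis, Grade ≥3 | resume at Grade ≤2 | resume on resolution | differs |
| Liver, Grade 1 | maintain | maintain | agrees |
| Liver, first Grade 2 | maintain | maintain | agrees |
| Diarrhoea, tolerable Grade ≤2 | maintain | maintain | agrees |
| Diarrhoea, first Grade ≥3 | resume at Grade ≤2 | resume at Grade ≤2 | agrees |

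Tally: 4 opposed + 4 different + 4 in agreement = 12.

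**Delay caps.** Table 2 uses more than 56 days; the diarrhoea and colitis rows of Table 3 use more than 2 cycles. With 28-day cycles (section 6.1.1), 2 × 28 = 56 days, so the caps agree.

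**Search for a precedence rule.** Table 2's footnote and the triple-asterisk footnote in Table 3 point only to the hepatitis B guidance. The closing notes send discontinuation questions to the Principal Investigator but do not rank the tables. Section 7.8 directs staff to section 6 and refers to the Principal Investigator only events the protocol does not describe; these events are described twice.

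**Can Table 3 simply replace Table 2 on combination?** No. Table 3 gives no ublituximab instruction for neutropenia, thrombocytopenia or other non-haematological events, so Table 2 is still needed.

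**How many patients? Illustration only.** Section 1.1.2 reports Grade 3/4 pneumonia in 8% of 75 combination patients and pneumonitis in 2 of 75 (2.7%). The number reaching combination here is an assumption: if 50% or 30% of 24 are in complete response after induction, 24 × 0.50 = 12 or 24 × 0.70 = 16.8, about 17.

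- At 8%: expected 12 × 0.08 = 0.96 to 17 × 0.08 = 1.36; chance of at least one, 1 − 0.92^12 = 0.63 to 1 − 0.92^17 = 0.76.
- At 2/75: expected 12 × 2/75 = 0.32 to 17 × 2/75 = 0.45; chance of at least one, 1 − (73/75)^12 = 0.28 to 1 − (73/75)^17 = 0.37.

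The spread shows that the answer depends on the rate borrowed, and neither rate comes from untreated patients.

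**The case against.** The best defence is that the specific rule displaces the general one. Table 3 applies only to patients taking umbralisib, its rows name ublituximab by organ, and Table 2 has a single catch-all row. The section already works this way once: a bullet requires permanent discontinuation for Grade 4 anaphylaxis, although Table 2's Grade 3-or-higher row taken alone would allow resumption. Section 6.1.2 also opens by making dosing conditional on acceptable clinical and laboratory findings, and the trial has one site. This is a sensible reading, but the protocol never states it, and investigator discretion in Table 2 attaches only to its Grade 3-or-higher row.

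Several stronger readings are tempting and are not supported:

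- **That all four organ groups carry opposite instructions.** Liver has no opposed cell. At Grade 3 or higher, waiting for Grade 1 or lower can satisfy both tables, because Table 2 leaves the withholding to the investigator.
- **That hepatitis B is the only exception to Table 2's general rule.** The anaphylaxis bullet is another.
- **That the closing note flatly contradicts the pulmonary row.** The same paragraph foresees stopping both drugs after discussion with the Principal Investigator. What remains is a need for alignment.
- **That the footnote means stopping the antibody for good while umbralisib continues.** That is drawn from silence, could arise only at Grade 3 or higher, and concerns a discretionary permission.
- **That the primary endpoint is compromised.** Complete response counts at any time during treatment. After the first combination cycle ublituximab is given once per 28-day cycle to Cycle 6 and then only at Cycles 9 and 12, so a short hold may miss no dose. No effect on the response rate has been shown.
- **That about one affected patient is to be expected.** The 8% comes from relapsed or refractory patients with a median of 3 prior therapies; this trial treats untreated patients for a fixed 12 cycles with required prophylaxis.

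**Conclusion.** The point holds for four directly opposed situations out of 12: pulmonary Grade 1-2, pulmonary Grade 3 or higher, colitis Grade 1-2, and intolerable or persistent Grade 2 diarrhoea. Four further situations differ without direct opposition, and the rest agree, as do the delay caps. It rests on the wording alone and on Table 2 not being restricted to induction; it needs no assumption about event rates. The passages should be reconciled because, as written, they disagree on whether a drug is permanently stopped for a serious event. The closing note and the sinopulmonary footnote are a lesser point. Patient numbers are illustrative, and nothing is claimed about the complete response rate or power.

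**What to change.** Amend section 6.1.2 in two places.

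1. Add a precedence statement: during combination treatment, where Tables 2 and 3 both give a ublituximab instruction for the same event, the table named by the sponsor governs; where Table 3 gives none (neutropenia, thrombocytopenia, other non-haematological events), Table 2 applies. Cross-reference it from both tables, as is already done for hepatitis B. Simply restricting Table 2 to induction would not work, because ublituximab would then have no cytopenia rules on combination.
2. Align the closing note on continuing umbralisib, and the sinopulmonary footnote, with the pulmonary Grade 3-or-higher row, so that each is explicit about both drugs and consistent with the Principal Investigator discussion already required.

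Which instruction is clinically right in any cell is for the sponsor to decide. The cost is wording in one section, with the amendment approvals that section 13.2 requires; no new procedures, visits or data are needed.

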6.2 STUDY AGENT ACCOUNTABILITY PROCEDURES AND OVERVIEW

Ordering Ublituximab and Umbralisib

Ublituximab and TGR-1202 (umbralisib) are available from TG Therapeutics, Inc. Please allow 5 to 7 business days between drug ordering and drug arrival. Order ublituximab Monday through Wednesday to ensure shipment does not arrive on a weekend day. Ensure staff will be available to unpack shipment immediately upon arrival. Please direct drug orders to [contact]. The email should include the following:

- Requested quantity of TG Therapeutics, Inc. study drug(s)
- Date needed
- Principal Investigator name
- Study title
- TG Therapeutics, Inc. tracking number (U2-NTG-009)
- Investigational drug pharmacy shipping address
- Total number of study subjects enrolled to date
- Number of study subjects currently receiving each TG Therapeutics agent

Upon receipt of this shipment, the clinical trial designee at our site will update the accountability forms for both ublituximab and umbralisib. If there is any abnormality in the supplied boxes (ublituximab) or bottles (umbralisib), the Pharmacist or designee will document it during the acknowledgement of receipt and contact TG Therapeutics, Inc. at [contact].

The Drug Accountability Log will record the study drugs received, dosages prepared, time prepared, doses dispensed and doses/vials destroyed. The Drug Accountability Log will be reviewed during any site visits and at the completion of the study.

STUDY MEDICATION OVERVIEW

Ublituximab

Chemical Name: ublituximab

Other Names: TG-1101

Classification: Recombinant chimeric anti-CD20 monoclonal antibody

Mode of Action: Targets CD20 antigen on B-cells

Description: Ublituximab is a genetically engineered chimeric murine/human mAb directed against the CD20 antigen found on the surface of B lymphocytes.

Ublituximab displays the typical structure of immunoglobulins, consisting of two gamma (γ) heavy chains and two kappa (κ) light chains linked by disulfide bridges. It is composed of a murine variable region (37.2% of total amino acids) fused onto human constant regions.

How Supplied: Concentration of 25mg/mL in 6 mL (150 mg) and 36 mL (900 mg) single-use glass vials.

Storage: Ublituximab vials must be stored in a secured, limited-access, refrigerated area at a temperature ranging from 2-8°C (36-46°F). Ublituximab must not be frozen. Temperature should be monitored, documenting minimum and maximum daily.

Stability: Once a vial of ublituximab has been diluted, it must be used immediately or be stored refrigerated. The storage duration of ublituximab diluted in polyvinyl chloride (PVC) or non-PVC polyolefin (PO) material is up to 24 hours when refrigerated at 2-8°C (36-46°F). After allowing the diluted bag to come to room temperature, use immediately.

Expiration memorandums will be provided noting lot expiration dates. For questions about expiry email [contact].

Route of Administration: Intravenous

Packaging: Ublituximab is packed in kits. Each kit contains:

- Six vials containing 150 mg solution of ublituximab in each or
- One vial containing 150 mg solution of ublituximab (for replacement if needed), or
- One vial containing 900 mg solution of ublituximab

The container closure system of ublituximab is a type I glass vial closed by a siliconized chlorobutyl rubber stopper and a tamperproof protective cap crimped to the neck of the vial

Availability: Ublituximab is available from TG Therapeutics, Inc.

Umbralisib (TGR-1202)

Classification: Dual inhibitor of Phosphatidylinositol-3-Kinase (PI3K) Delta and CK1 epsilon

Formulation: See Investigator Brochure

Mode of Action:	Irreversibly inhibits activity of the Class I Delta isoform of PI3K
How Supplied:	Umbralisib: 200 mg tablets
Storage:	Umbralisib must be stored in a secured limited-access area between 20°C and 25°C. Excursions permitted between 15°C and 30°C. Do not freeze.
Stability:	Expiration memorandums will be provided noting lot expiration dates. For questions about product expiry email [contact] .
Route of Administration:	Oral
Packaging:	Umbralisib is provided in HDPE bottles each containing 30 tablets and a silica gel canister as a desiccant.
Availability:	Umbralisib is available from TG Therapeutics, Inc.

